7.4 Assessment of Pharmacokinetics

No pharmacokinetics determinations will be assessed during this study.

7.5 Assessment of Safety

7.5.1 Adverse Events

7.5.1.1 Adverse Events Assessments

An AE is an untoward medical occurrence in any subject during the study which does not necessarily have a causal relationship with the study drug treatment. Adverse events can be categorized as treatment-emergent or treatment-related. All AEs will be recorded and will be documented in the eCRF and will be captured from the time of intake of study drug. All serious adverse events (SAEs) will be captured from the time of signing the ICF and must be reported to the sponsor within 24 hours of awareness. The condition of the subject will be monitored throughout the study for any signs or symptoms. The occurrence of AEs should be sought by

nondirective questioning of the subject at each visit during the study. All AEs will be collected as:

- The subject's response to questions about their health
- Symptoms spontaneously reported by the subject
- Clinically relevant changes and abnormalities observed by the investigator (eg, local and systemic tolerability, laboratory measurements, results of physical examinations)

If a Medical History condition worsens or increases in frequency after the first dose of IP, it should be recorded as an AE in the eCRF. If an AE worsens in intensity, it should be recorded as a new AE. Otherwise, it continues as the first report (counted as the same AE) until the subject is recovered.

The investigator or designee will record the following on the AE eCRF:

- AE and relevant clinical findings
- Time/date of onset
- Time/date of recovery
- Intensity
- Action taken on study drug/treatment
- Other action taken to treat the event
- Relation to study drug/treatment
- Seriousness of the AE

AEs requiring therapy must be treated with recognized standards of medical care to protect the health and well-being of the subject. Treatment due to an AE will be recorded.

Subjects who prematurely withdraw from the study for AEs are to be monitored for up to 30 days after the subject stopped study treatment or until the abnormal parameter resolves or stabilizes.

The outcome of an AE will be classified as recovered, recovered with sequelae, not yet recovered, or death.

7.5.1.2 Timing

Adverse events will be assessed at all study visits. Adverse events should be monitored by the investigator for up to 30 days after the subject has stopped study treatment or until the AE has resolved or stabilized.

Treatment-emergent AEs (TEAEs) include any untoward medical occurrence in a patient/subject or clinical investigation subject after administration of an investigational study treatment, which does not necessarily have to have a causal relationship with this treatment. A TEAE can therefore be any unfavorable and unintended sign (including an abnormal laboratory finding), symptom, or disease temporally associated with the use of the product, whether or not related to the medicinal (investigational) product. It could also include accidents and reasons for changes in medication (drug and/or dose), any medical, nursing or pharmacy consultation, or admission to hospital or surgical operations. Record TEAEs that occur after the first dose through 5 days after the last dose.

Treatment-related AEs are all TEAEs that are considered by the investigator as causally related to administration of the study drug.

7.5.1.3 Severity of Adverse Events

The investigator is to classify the severity (intensity) of an AE according to the following definitions:

- Mild – The subject was aware of the signs and symptoms but the signs and symptoms were easily tolerated.
- Moderate – The signs and symptoms were sufficient to restrict, but did not prevent, usual daily activity for the subject.
- Severe – The subject was unable to perform usual daily activity.

The maximum intensity of an AE (mild, moderate, or severe) will be assessed taking into account the possible range of intensity of the symptom(s).

The severity of diarrhea and lymphocytopenia will be graded using a modified common terminology criteria for adverse events (CTCAE), Version 4.03 (see [Appendix 9](#)). If the subject reports that they are experiencing diarrhea, they will be presented with the Bristol Stool Chart and asked to identify the consistency (see Bristol Stool Chart [Appendix 10](#)). Only Type 7 on the Bristol Stool Chart is considered diarrhea. The frequency of Type 7 diarrhea is then used to determine the CTCAE grade. All subjects will be provided with educational materials at Baseline to help prepare them for the potential GI-related adverse events. All subjects will be asked at Baseline to assess the average frequency of their bowel movements for the past 15 days and the general consistency of the stool using the Bristol Stool Chart.

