- ALT or AST $>3\times\text{ULN}$ with concurrent appearance or worsening of fatigue, nausea, vomiting, right upper quadrant pain or tenderness, fever, rash, or eosinophilia ($>5\%$ eosinophils on differential leukocyte count)
- Serum creatinine $>1.5\times\text{ULN}$ on repeat exam (if assumed increase is related to study drug)
- Proteinuria measured as 3+ or above in urine dipstick on 2 consecutive samples, 4 weeks apart
- If advised by the Medical Monitor or PML experts.

Laboratory tests can be repeated earlier than the next scheduled consecutive visit at the investigator's discretion and any associated safety issue should be followed up as per the Investigator's clinical judgment until resolution/stabilization.

Replacement Policy

Subjects who prematurely discontinue from the study after randomization will not be replaced.

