7.5.1.5 Adverse Event of Special Interest (AESI)

If the subject complains of any kind of neurological symptoms (such as aphasia, clumsiness, weakening of arms and legs or any new neurological signs or symptoms) during the scheduled study visits or at any time point during the study, the subject will be evaluated at the site for any neurological dysfunction. If the site evaluation for neurological dysfunction is positive or equivocal, the subject will be referred to a neurologist for consultation. If the subject is negative for PML after examination by the neurologist, the subject will continue in the study. If required, the PML experts will be consulted to assess and monitor, as the case may be. The study drug will be stopped in the subject only if recommended by the PML expert.

Stopping Rules:

The potential event of PML will be carefully managed by utilizing the below stopping criteria. If one or more of the below criteria are met, study drug will be permanently discontinued and the subject will be scheduled for an ETV followed by Safety Follow-up visits 1 week (\pm 3 days) after the last dose of study drug.

- Lymphocytes <500/mm³ in one reading;
- Lymphocytes <800/mm³ in 3 consecutive visits 4 weeks apart; Lymphocyte count can be repeated in the interim period. If the interim lymphocyte counts are higher than 800/cu.mm, then the PI with concurrence from Medical monitor, will decide if the subjects should stay in the study or discontinued from the study.
- When recommended by the PML expert.

Blood collection for lymphocyte subset & Ab titer can be collected at any study visit if the subject shows signs of PML.

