### 11.4 Analysis Visit Window

Efficacy and safety endpoints will be analyzed according to their windowed visits defined by actual study day. If more than one visit occurs within a single visit window, then the analysis will take the one closest to the target day. If the 2 visits are equidistant from the target day, the later visit will be used. A later visit within the window will be used for LOCF.

The following analysis visit windows will apply:

Visit	Week	Target Day	Efficacy Assessment Window	Safety Assessment Window
2	Baseline	0	On or prior to date of first dose	On or prior to date of first dose
3	4	28	Post-dose – Day 42	Post-dose – Day 42
4	8	56	Day 43 – Day 70	Day 43 – Day 70
5	12	84	Day 71 – Day 98	Day 71 – Day 98
6	16	112	Day 99 – Day 126	Day 99 – Day 126
7	20	140	Day 127 – Day 154	Day 127 – Day 154
8	24	168	≥Day 155	≥Day 155
9 (Follow-Up)	25	LD+7	> LD+15	> LD+15

LD = Last dose date

Visits 3 through 8 are on-treatment visits. Therefore, only on-drug assessments or assessments performed within 15 days post last dose are to be analyzed within those windows, according to their actual study day. Visit 9 is an off-treatment visit, which will be analyzed according to their number of days after last dose, regardless of the actual study day. For example, a subject who has Visit 4 on Day 56, then discontinues with last dose on Day 84 and returns for Early Termination on Day 100 will have no data within the Visit 6 window. The Early Termination visit must be analyzed as Visit 9. For this subject, data for Visits 5, 6, 7, and 8 would be carried forward from Visit 4 in an LOCF analysis. If the last dose date is unknown, then all visits will be analyzed as on-treatment based on actual study day (i.e., no Visit 9 will be identified for the subject).

Subjects who permanently discontinue the study drug for any reason or who withdraw from the study prematurely prior to the end of the Double-Blind Treatment Period should undergo the ETV followed by the EOS Safety Follow-up Period Visit. In the event that the ETV or Week 24 Visit occurs > 1 week following the last dose of the study drug, the EOS Safety Follow-up Visit may not be required. If necessary, the Investigator may decide to extend the EOS Safety Follow-up Visits beyond 1 week to monitor recovery of safety parameters (eg, lymphopenia).

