For the 3 arms receiving active treatment, exposure-adjusted incidence rate will be defined for both titration and treatment periods as number of subjects with AEs divided by total number of subject-days with exposure to study medication. Total number of subject-days with exposure in each period = sum of durations in days across all subjects in each period. Duration in each period is defined as following:

- PPC-06 400 mg QD:
  - Titration period = Number of days between date of first study application and the earlier of date of last study medication and Day 14 inclusive
  - Treatment period = Number of days between Day 15 and date of last study application inclusive
- PPC-06 400 mg BID, PPC-06 600 mg BID:
  - Titration period = Number of days between date of first study application and the earlier of date of last study medication and Day 35 inclusive
  - Treatment period = Number of days between Day 36 and date of last study application inclusive

Summaries of the incidence of TEAEs will be displayed by treatment according to the following:

- All TEAEs by SOC in alphabetical order and PT in descending order of frequency (the combined frequency in the three active treatments)
- All TEAEs by SOC, PT, and maximum severity (mild, moderate, or severe)
- All TEAEs by SOC, PT, and maximum causality (not related, related) to the study drug

At each level of summarization, a subject will be counted once if he/she reported one or more events. In the counts of subjects with TEAEs, each subject will contribute only once (maximum severity) regardless of the number of occurrences (events).

The severity of TEAEs and relationship to study drug will be summarized in a similar manner. For summaries of relationship to study drug, a subject will be classified according to the closest relationship. For summaries of TEAE severity, a subject will be classified according to the highest severity.

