## **12.9.2 Clinical Laboratory Testing**

Clinical laboratory values will be reported as complete listings of individual subject data. All laboratory values will be classified as normal, low, or high based on normal ranges supplied by the laboratory. Subjects with values outside the normal range will be flagged and summarized using shift tables. A separate listing and table will identify and summarize subjects with markedly abnormal values. For quantitative measures, observed and changes in clinical laboratory values will be analyzed descriptively by time of collection and treatment group.

Additionally, lymphocyte counts will be summarized by clinical response of PASI-50 and PASI-75 (Yes/No) at Week 24. Lymphocyte counts and hs-CRP will also be plotted against PASI scores by visit and treatment. The correlation coefficient will be reported.

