14.3.2.3.1	Summary of Lymphocyte Counts by Clinical Response of PASI-50 at Week 24, Safety Population
14.3.2.3.2	Summary of Lymphocyte Counts by Clinical Response of PASI-75 at Week 24, Safety Population
14.3.2.4.1	Clinical Laboratory Results, Shifts from Baseline by Visit, Chemistry, Safety Population
14.3.2.4.2	Clinical Laboratory Results, Shifts from Baseline by Visit, Hematology, Safety Population
14.3.3.1	Summary of Vital Signs by Treatment and Visit, Safety Population
14.3.3.2	Summary of Vital Signs, Shifts from Baseline by Visit, Safety Population
14.3.4	Summary of ECG Results by Treatment and Visit, Safety Population
Figures	
14.3.1.1	Plot of Mean Change from Baseline by Visit, Lymphocyte Counts vs PASI scores, Safety Population, PPC-06 400 mg QD
14.3.1.2	Plot of Mean Change from Baseline by Visit, Lymphocyte Counts vs PASI scores, Safety Population, PPC-06 400 mg BID
14.3.1.3	Plot of Mean Change from Baseline by Visit, Lymphocyte Counts vs PASI scores, Safety Population, PPC-06 600 mg BID
14.3.1.4	Plot of Mean Change from Baseline by Visit, Lymphocyte Counts vs PASI scores, Safety Population, Placebo
14.3.2.1	Plot of Mean Change from Baseline by Visit, hsCRP vs PASI scores, Safety Population, PPC-06 400 mg QD
14.3.2.2	Plot of Mean Change from Baseline by Visit, hsCRP vs PASI scores, Safety Population, PPC-06 400 mg BID
14.3.2.3	Plot of Mean Change from Baseline by Visit, hsCRP vs PASI scores, Safety Population, PPC-06 600 mg BID
14.3.2.4	Plot of Mean Change from Baseline by Visit, hsCRP vs PASI scores, Safety Population, Placebo
Listings	
16.1.7	Subject Enrollment and Randomization, All Randomized Subjects
16.2.1.1	Screen Failure, All Screen Failure Subjects
16.2.1.2	Subject Disposition, All Randomized Subjects
16.2.2	Protocol Deviations, All Randomized Subjects
16.2.3	Population Datasets, All Randomized Subjects
16.2.4.1	Demographics and Baseline Characteristics, All Randomized Subjects
16.2.4.2	Prior and Concomitant Medication, All Randomized Subjects
16.2.4.3	Psoriasis Treatment History, All Randomized Subjects
16.2.4.4	Concurrent Procedures, All Randomized Subjects
16.2.4.5	Medical History, All Randomized Subjects

16.2.4.6	Psoriasis Medical History, All Randomized Subjects
16.2.5.1	Study Drug Accountability – Blister Packs, All Randomized Subjects
16.2.5.2	Study Drug Accountability – Bottles, All Randomized Subjects
16.2.5.3	Study Drug Exposure and Compliance, All Randomized Subjects

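### CTCAE grades for lymphopenia and diarrhea are listed but not tabulated, no planned table counts subjects per arm below 800 or 500 lymphocytes/mm³, and the promised markedly abnormal laboratory table has no criterion and no Section 16 entry

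*Protocol*

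**What the plan says.** **Grading.** Protocol 7.5.1.3 defines severity by symptoms and daily activity ("Mild – The subject was aware of the signs and symptoms but the signs and symptoms were easily tolerated") and adds for two events: "The severity of diarrhea and lymphocytopenia will be graded using a modified common terminology criteria for adverse events (CTCAE), Version 4.03". Appendix 9 puts lymphocytes below 500/mm³ at Grade 3 and below 200/mm³ at Grade 4. Protocol 7.5.1.5 makes "Lymphocytes <500/mm³ in one reading" a stopping criterion, as does 5.4. Both sections also contain a rule for counts below 800/mm³ at three consecutive visits.

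**Adverse event tables.** SAP 12.9.1 plans "All TEAEs by SOC, PT, and maximum severity (mild, moderate, or severe"), and the shell of Table 14.3.1.3 has only those three levels. The CTCAE grade appears in Listings 16.2.7.1 to 16.2.7.3, in a column separate from Severity.

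**Laboratory tables.** SAP 12.9.2 classes values as low, normal or high against the laboratory's range. The planned hematology outputs are by-visit summary statistics (Table 14.3.2.2), lymphocytes by PASI response (Tables 14.3.2.3.1 and 14.3.2.3.2) and "Clinical Laboratory Results, Shifts from Baseline by Visit, Hematology, Safety Population". SAP 12.9.2 also commits to more: "A separate listing and table will identify and summarize subjects with markedly abnormal values". Protocol 8.8.2 makes the same commitment.

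**Choice of value.** SAP 11.4 covers efficacy and safety endpoints alike: "If more than one visit occurs within a single visit window, then the analysis will take the one closest to the target day". Protocol 5.4 expects extra values: "Laboratory tests can be repeated earlier than the next scheduled consecutive visit at the investigator's discretion". Protocol 7.5.3 calls for a repeat within 2 weeks after a significant shift.

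**The concern.** This trial compares three doses of a drug whose class, by Protocol 5.4, affects lymphocyte counts and can harm liver and kidney at excessive exposure. Protocol 8.8 rests the safety assessment mainly on AE frequency and on counts of laboratory values outside set ranges. The natural question for each dose is how many subjects fell below 800/mm³ and how many below 500/mm³.

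The planned tables do not answer it. The severity table uses a scale into which no cell count enters, the shift tables merge all depths of lymphopenia, and the by-visit rule can leave out a subject's worst value. The one table that could close the gap is promised without a definition. If its cut-offs are chosen after unblinding, they are post hoc.

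**Working it through.** The plan states no figure to reproduce. The check sets each planned output against the protocol's grades and levels.

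**1. What the shift table can separate.** The documents give no lower limit of normal (LLN) for lymphocytes, so it is assumed and varied over 800, 1000, 1200 and 1500/mm³. The SAP class is Low if the count is below the LLN. Grades are from Appendix 9.

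| Count/mm³ | Appendix 9 grade | Below 500? | SAP class |
|---|---|---|---|
| 150 | 4 | yes | Low at every LLN |
| 450 | 3 | yes | Low at every LLN |
| 499 | 3 | yes | Low at every LLN |
| 500 | 2 | no | Low at every LLN |
| 650 | 2 | no | Low at every LLN |
| 790 | 2 | no | Low at every LLN |
| 900 | 1 if LLN is 1000 or more | no | Normal at LLN 800, otherwise Low |
| 1100 | 1 if LLN is 1200 or more | no | Normal at LLN 800 or 1000, otherwise Low |

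Grades 2 to 4 always share one class, and Grade 1 joins them once the LLN exceeds 800. By-visit counts of Low also cannot show whether the same subject was below 800/mm³ at three consecutive visits.

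**2. What the severity table can separate.** Mild, moderate and severe turn on awareness, tolerance and restriction of activity. Nothing in either document maps a CTCAE grade to these levels. A count below 500/mm³ without symptoms, if reported as an AE, may be entered as mild. If only the grade is entered, SAP 12.9.1 puts the event under missing severity.

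**3. Whether another output gives the count.** The by-visit minimum can show that at least one subject was below 500/mm³, but not how many. Preferred-term incidence and discontinuation counts carry no grade or level. The disposition shell has only an adverse-event row. For the markedly abnormal laboratory table, SAP 12.9.2 gives no cut-off (numeric cut-offs exist only for vital signs, in 12.9.3) and Section 16 has neither an entry nor a shell. The nearest output is Listing 16.2.8.3, on values outside the normal range. SAP Section 13 does not declare the omission. Urinalysis, which carries the proteinuria criterion of 5.4, is listed but not tabulated.

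**4. What the window rule does to repeats.** Inputs: a scheduled visit at *d* = −3 to +3 days from target (Table 1-1), a repeat *k* = 1 to 14 days later (7.5.3), and a window from −13 to +14 days (SAP 11.4; for example Days 43 to 70 around Day 56), with ties going to the later visit. That gives 7 × 14 = 98 combinations.

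- The repeat replaces the scheduled value when |*d* + *k*| ≤ |*d*|. This needs *d* < 0 and *k* ≤ 2|*d*|, so 6 + 4 + 2 = 12.
- The repeat falls in the next window when *d* + *k* > 14: 1 + 2 + 3 = 6 (for *d* = 1, 2, 3). It then lies 11 to 13 days before the next target and loses to a scheduled visit within 3 days, if that visit takes place.
- The repeat loses inside its own window in the remaining 98 − 12 − 6 = 80.

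So the repeat stays out of the by-visit tables in 80 + 6 = 86 of 98 if the next visit is attended, and the scheduled value drops out in 12. Either can be the lower one. Separately, an early termination visit more than 15 days after the last dose is analysed as Visit 9, while the laboratory shells end at Week 24.

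**The case against.** The SAP already commits to a table of markedly abnormal values, and Section 16 is only an outline. The data are not lost: AE listings by arm carry the CTCAE grade, and Listing 16.2.8.2.4 is devoted to lymphocytes. All of that stands. The gap is in tabulation, not in collection.

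Four stronger readings are tempting, and the documents support none of them.

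- *The dose-response for lymphopenia cannot be read.* By-visit means, minima, changes and shifts to Low are all given by arm, as are preferred-term incidence and a lymphocyte plot per arm. What is missing is the number of subjects at each depth.
- *CTCAE replaces the symptom scale, and a symptom-free low count must then be mild.* The listings hold both columns, so both are recorded. The definition of mild assumes that the subject notices something, so a silent count strictly fits no level. Mild is a possible entry, not a necessary one. For diarrhea the functional scale is meaningful in itself.
- *One of two values is always lost.* The 98 combinations are a grid of timings, not probabilities. The scheduled value is kept in 86. A repeat in the next window survives if that visit is missed. The omission concerns by-visit summaries only, and the criterion of below 500/mm³ needs a single reading.
- *Counting subjects who cross a level counts those who met a stopping criterion.* Most criteria in 5.4 carry conditions: consecutive visits, repeat examination, assumed relation to drug, or two urine samples four weeks apart.

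**Conclusion.** The concern holds as a gap in planned tabulation and should be corrected. Protocol 7.5.1.3 calls for a graded severity that no SAP table uses. No listed or shelled table gives, by arm, the number of subjects at each lymphocyte grade or below 800 or 500/mm³. A table promised in both documents lacks a criterion and an entry.

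The size is up to four lymphocyte grades merged into one class, and early repeats outside the by-visit tables in most of the timings examined. The first result holds for every LLN assumed from 800 to 1500/mm³. The second assumes attended visits within 3 days of target and repeats within 14 days. How often a low count would be entered as mild cannot be derived from the documents. It depends on whether sites report it as an AE and how they fill in the severity field.

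The efficacy analyses are not affected.

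**What to change.** 1. In SAP 12.9.1, add a by-arm table of lymphopenia and diarrhea TEAEs by maximum CTCAE grade, beside the mild/moderate/severe table.
2. In SAP 12.9.2, add a by-arm table of the worst post-baseline lymphocyte count by Appendix 9 grade, using all post-baseline values including unscheduled and early termination visits. State that the one-value rule of 11.4 applies only to by-visit summaries.
3. In SAP 12.9.2, define markedly abnormal for laboratory values with the numeric levels already in Protocol 5.4, used only as reporting categories: lymphocytes below 800 and below 500/mm³, ALT or AST above 3, 5 and 8 times ULN, creatinine above 1.5 times ULN, urine protein 3+ or above. Label these as ever crossed the level. Count separately the subjects who met the full 5.4 criterion with its conditions, and enter the table in Section 16.

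For the second count in item 3, note that 7.5.1.5 adds a provision for interim counts above 800/mm³ that 5.4 does not contain. The two passages must be reconciled so that the count has one definition.

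The cost is SAP wording and two or three extra tables from data already collected, with no added burden on subjects. The definitions should be fixed before unblinding.
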